2 OBJECTIVES

The goal of the study is to assess the symptom burden and baseline clinical and economic characteristics in COPD patients treated with the single-inhaler dual therapies UMEC/VI or FLUT/SAL.

2.1 Primary

- The primary objective is to compare patient-reported COPD symptom burden among patients treated with UMEC/VI to those treated with FLUT/SAL.

2.2 Secondary

The secondary objectives are to:

- Describe baseline all-cause, COPD-related, and exacerbation-related health care resource utilization, costs, and clinical characteristics (e.g., comorbidities, treatment history) in patients treated with UMEC/VI or FLUT/SAL.
- Identify the GOLD classification of patients treated with UMEC/VI or FLUT/SAL.

3 RESEARCH METHODOLOGY

3.1 Study Design

This is a cross-sectional observational survey study of adult Medicare Advantage enrollees with evidence of COPD diagnosis and treatment. Cross-sectional survey data will be linked with retrospective claims data for the 12-month period (baseline) prior to the survey. An image illustrating the study process is provided in the Appendix.

¹¹ Celli BR, Decramer M, Wedzicha JA, et al. An Official American Thoracic Society/European Respiratory Society Statement: Research Questions in Chronic Obstructive Pulmonary Disease. *Am J Respir Crit Care Med.* 2015;191:e4-e27.

The study will use a health plan recruitment strategy. Use of this strategy requires that the health plan affiliated with Optum approve the study concept. Optum will also work with a central institutional review board (IRB) to obtain appropriate approvals for the study.

Study subjects will be identified using enrollment, medical, and pharmacy records from Optum's proprietary research claims database (ORD). A target population of 2,700 potential study participants will be contacted directly by mail. Patients will be asked to return the study survey if they consent to participate. The survey will collect information on patients' COPD duration, current treatment, symptoms, burden of illness, smoking history, and demographic and sociodemographic characteristics. Based on informal testing of the study instrument, the estimated time for survey completion is 10 minutes. Based on previous cross-sectional patient survey studies conducted by Optum, an overall response rate of 30-35% is expected.¹²

Following completion of data collection, results of the survey will be merged with claims data covering the 12-month baseline period for analysis. Pharmacy and medical claims data will be used to calculate all-cause and COPD-related health care utilization and costs, treatment patterns, and baseline clinical characteristics. Descriptive, IPTW, and multivariable statistical methodologies will be used.

3.1.1 Health Plan Notification

Optum will send a research study notification letter to the health plan market medical directors to alert them that a survey research study is being conducted in the field. In addition, Optum will send a courtesy letter to affiliated health plan physicians currently treating the identified patients to notify them that one or more of their patients is being invited to take part in the study.

3.1.2 Patient Invitation

Patient names and addresses will be obtained from the most recent contact information recorded in the enrollment data. Identified patients will receive a patient invitation letter on health plan and Optum letterhead, signed by the National Medical Director (NMD) of the health plan and senior research director of Optum, inviting them to participate in the survey study. The letter will describe the goals of the study, explain that participation is voluntary, and provide instructions for completing and returning the patient questionnaire.

A total of \$25 in post-paid compensation in the form of a pre-paid debit card will be mailed to subjects who return the study survey.

3.1.3 Study Start-Up Data Collection Services

A survey research vendor will be utilized to handle data collection and management activities. The survey research vendor will be required to comply with the established practices of Optum as specified in their contract. Procedures relating to data handling and data transfers, database set-up, ID encryption, confidentiality, data quality management, and documentation will be specified by Optum. The vendor will be responsible for the following:

- Printing subject materials
- Shipping and tracking all subject materials
- Tracking, mailing, and reconciling post-paid debit card distribution to participants
- Complying with confidentiality procedures
- Developing the study database and entering data in accordance with the Optum's specifications
- Securely transferring the database to Optum per Optum's SOPs

¹² Goolsby Hunter A, Brenneman S, Brekke L. Response Rates in Direct-to-Patient Surveys. Presented at the 20th Annual Meeting of the International Society of Pharmacoeconomic Research (ISPOR); Philadelphia, May 17-20, 2015.

3.1.4 Patient Survey Implementation

The study survey packet containing the invitation letter printed on letterhead, the IRB-approved statement of informed consent, the approximately 6-page survey instrument printed in booklet form, and postage-paid business reply envelope will be sent to approximately 2,700 patients in total. All study participants will be mailed a reminder postcard two weeks following the initial mailing. The postcard will thank those participants who have completed and returned their survey and encourage those who have not yet completed their survey to do so.

Four weeks following the initial mailing, a second study packet will be sent to survey non-responders. This packet will include a second version of the study invitation letter, the IRB-approved consent statement, the survey instrument booklet, and a postage-paid business reply envelope. Some respondents whose responses are missing for key elements of the survey will be contacted by mail to request completion of missing materials.

The mailings will be sent in a personalized envelope (i.e., the address is printed directly on the envelope) and first class postage will be used. Personalized survey materials and first-class postage have all been shown to increase response rates in mail surveys.^{i,ii}

Data collection will occur over the course of eight weeksⁱⁱⁱ. It is estimated that two waves of data collection will be needed to reach the target sample size. The same process and materials will be used for both waves of survey data collection (Wave 1 and Wave 2). While the survey is in the field, the number of completed surveys will be tracked on a weekly basis.

Overall, it is estimated 30-35 percent of patients will respond to the survey, yielding a final sample of 770 total completed surveys (approximately 385 per treatment group) based upon a sampling frame of 2,700 MA health plan members. Personalized thank-you letters will be mailed to every patient who completes the survey. The post-paid patient compensation of \$25 in the form of a pre-paid debit card will be included with the thank-you mailing.

3.1.5 Study Period

An illustrative example of the study period is provided in Figure 1, which includes the sample identification, claims observation, and data collection periods described below. The 12-month period used for claims sample identification corresponds to the 12-month baseline claims analysis period for each sample.

Study period dates are estimated based on the current timeline for sample identification; changes in timelines for study tasks prior to sample identification will have a corresponding impact on the timing of later tasks.

Sample Identification Period

The sampling frame of COPD patients will be identified in Optum's research database using administrative claims data from the most recently available 12-month period at the time of sample identification, defined as the *claims sample identification period*. This period is estimated to begin 01 Jun 2017 and end 31 May 2018 for Wave 1 survey administration. This will ensure that the study sample is identified based on the most recently available pharmacy data in Optum's research database at the estimated time of identification (estimated as mid-June for Wave 1).

Medical claims for the full 12-month period will be accessed for sample identification; however, only a portion of those are complete, fully adjudicated claims. However, due to the approximate 6-month medical claims lag and 6-week pharmacy claims lag, fully complete medical and pharmacy claims data during this time period will not be available for all patients at the time of sample identification. An estimated 6 months of complete, fully adjudicated medical claims data will be available at the time of identification (01 June 2017 to 30 November 2017), with partially adjudicated claims available for the

latter 6 months of the sample identification period (01 December 2017 – 31 May 2018). Following completion of the claims lag, fully adjudicated medical claims will be accessed for the Claims Observation Period as described below. The sample identification period and the claims observation period will cover the same 12-month period for each wave of the survey.

Claims Observation Period

The baseline claims observation period will be the 12-month period closest to and prior to sample identification. The observation period for Wave 1 is estimated to be 01Jun2017-31May2018.

[figure not shown]
Eligible survey respondents' complete medical and pharmacy claims data during the 12-month baseline period will be extracted for creation of the merged analytic file following completion of the 6-month medical claims lag for the latter administration (Wave 2).

Dates provided above are estimates for Wave 1; the same process and lags will apply for the subsequent sample identification period and claims observation period for Wave 2. Final identification and observation period dates will be provided in the statistical analysis plan (SAP).

Survey Fielding Period

Assuming sample identification is completed in June 2018, the 8-week survey fielding period will begin in late June-early July 2018 continue through late August-early September 2018 (Wave 1). Final survey fielding dates for Wave 1 and Wave 2 will be provided in the SAP.

Figure 1 - Study Period: Rolling Sample Identification for 12-month Baseline Claims Data Linked to Cross-sectional Survey Data

3.1.6 Link to Administrative Claims Data

Following completion of survey data collection activities for both waves and the 6-month medical claims lag, 12 months of surveyed patients' pharmacy and medical claims data for the baseline period will be re-extracted. Continuous health plan enrollment and other exclusion criteria will be applied. Survey and health care claims data will be combined into a merged analytic file.

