3.2.1.2 Exclusion Criteria

- Patients with ≥2 diagnosis codes for asthma at least 30 days apart in the 12-month baseline period will be excluded. ICD-10-CM codes for identifying asthma are shown in Figure 4.

Figure 4 – Diagnosis Codes for Asthma

Code	Type	Description
J4520	ICD-10 Dx	Mild intermittent asthma, uncomplicated
J4521	ICD-10 Dx	Mild intermittent asthma with (acute) exacerbation
J4522	ICD-10 Dx	Mild intermittent asthma with status asthmaticus
J4530	ICD-10 Dx	Mild persistent asthma, uncomplicated
J4531	ICD-10 Dx	Mild persistent asthma with (acute) exacerbation
J4532	ICD-10 Dx	Mild persistent asthma with status asthmaticus
J4540	ICD-10 Dx	Moderate persistent asthma, uncomplicated
J4541	ICD-10 Dx	Moderate persistent asthma with (acute) exacerbation
J4542	ICD-10 Dx	Moderate persistent asthma with status asthmaticus
J4550	ICD-10 Dx	Severe persistent asthma, uncomplicated
J4551	ICD-10 Dx	Severe persistent asthma with (acute) exacerbation
J4552	ICD-10 Dx	Severe persistent asthma with status asthmaticus
J45901	ICD-10 Dx	Unspecified asthma with (acute) exacerbation
J45902	ICD-10 Dx	Unspecified asthma with status asthmaticus
J45909	ICD-10 Dx	Unspecified asthma, uncomplicated
J45990	ICD-10 Dx	Exercise induced bronchospasm
J45991	ICD-10 Dx	Cough variant asthma
J45998	ICD-10 Dx	Other asthma

- Patients with claims for both UMEC/VI and FLUT/SAL in the 6 months closest to sample identification will be excluded.
- Patients with claims for triple therapy will be excluded.
 - Triple therapy is defined as claims for formulations of ICS/LABA/LAMA, including combined monotherapy formulations and fixed dose combinations (FDC).
 - The impact of using same day fills, or 30 days, or 60 days between fills will be assessed at the time of sample identification.
- Patients with claims-based evidence of diagnosis or treatment for lung cancer during the 12-month baseline will be excluded from the final analytic sample following the claims lag.

Some exclusion criteria cannot be applied until after survey data collection and/or the medical claims lag are complete (e.g., patient-reported diagnosis and treatment, evidence of lung cancer). Criteria that can be applied at the time of sample identification will be applied at that time.

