3.3.1.3 Patient-reported COPD Symptom Burden

- **Dyspnea**—Breathlessness will be assessed using the Modified Medical Research Council Dyspnea scale (mMRC), a single item (0-4 scale) to assess patients' current level of dyspnea.^{iv,v} The mMRC is comprised of five statements that describe almost the entire range of respiratory disability from none (Grade 0) to almost complete incapacity (Grade 4). The score (Grade) is the number that best fits the patient's level of activity.
- **Burden of illness**—Condition-related well-being will be assessed using the COPD Assessment Test (CAT), an eight-item validated questionnaire developed by GSK to determine the impact of COPD on the patient's well-being and daily life.^{vi, vii} The items of CAT measure the most salient symptoms of COPD, including cough, chest tightness, breathlessness, and activity limitation attributed to COPD symptoms. Each of the items of CAT is scaled on a 0-5 point scale with higher values indicative of worse health status. The item response values of CAT are summed to produce a single score that ranges from 0 (best health status) to 40 (worst health status). The reference period is current.

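### The both-drug and triple-therapy exclusions stop at the end of the baseline claims window, and no rule applies them to current treatment as reported in the survey

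*Combined protocol and SAP*

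**What the plan says.** **Claims window.** Section 3.1.5 states: "The baseline claims observation period will be the 12-month period closest to and prior to sample identification". For the sample identification period it adds: "This period is estimated to begin 01 Jun 2017 and end 31 May 2018 for Wave 1 survey administration". The claims observation period covers the same 12 months. Identification itself is "estimated as mid-June for Wave 1". After the medical claims lag, Section 3.1.6 says that "pharmacy and medical claims data for the baseline period will be re-extracted"; nothing later is drawn.

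**Exclusions.** Section 3.2.1.2 states: "Patients with claims for both UMEC/VI and FLUT/SAL in the 6 months closest to sample identification will be excluded". It also excludes triple therapy, defined through claims, and leaves the allowed spacing between fills to be settled at sample identification. The synopsis places the triple-therapy exclusion in the baseline period.

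**Outcome.** Section 3.1.5 says that "the 8-week survey fielding period will begin in late June-early July 2018 continue through late August-early September 2018" for Wave 1. For CAT, Section 3.3.1.3 says: "The reference period is current". It describes mMRC as measuring the current level of dyspnea.

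**Check at the survey.** Self-reported treatment with one of the study drugs is an inclusion criterion (3.2.1.1). The survey asks for current COPD treatment (3.3.1.1). Patient-reported treatment is among the criteria applied after data collection (3.2.1.2), and its confirmation is a key element of a complete survey (4.2). The synopsis compares cohorts defined by self-report. Sections 3.4.1, 4.4 and 4.5 refer to treatment or treatment cohort without naming the source.

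**The concern.** The primary objective compares symptoms between patients on one dual therapy and patients on the other. The protocol treats triple therapy and use of both study drugs as disqualifying, but stops enforcing this before the outcome is measured.

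A FLUT/SAL patient who adds a LAMA after the window closes, or a UMEC/VI patient who adds an ICS, can still truthfully report the study drug. The CAT and mMRC on the enlarged regimen are then credited to dual therapy. The added class differs by cohort, and symptomatic patients are plausibly more likely to add one, so the error cannot be assumed to be neutral. The claims-based weighting covariates in Appendix 4 are baseline measures and cannot adjust for a later change. The sensitivity analysis named in Section 4.3 concerns exacerbation history, not regimen.

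**Working it through.** **1. The plan's own figures.** For a 95% interval of ±0.05 at p = 0.5, n = 1.96² × 0.5 × 0.5 / 0.05² = 384.15, rounded up to 385. This matches Figure 6. The low end of Figure 7 also reproduces: 1,350 × 0.30 = 405, and 405 × 0.95 = 384.75, about 385. At a 30% response and 5% ineligible there is no slack.

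**2. The gap.** The start point is 31 May 2018. The fielding phrases are read as calendar dates (my assumption):
- start of fielding, 21 June to 7 July: 21 to 37 days, about 3-5 weeks
- end of fielding, 20 August to 7 September: 81 to 99 days, about 12-14 weeks

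From sample identification in mid-June (15 June assumed) the gaps are shorter: 6 to 22 days (about 1-3 weeks) and 66 to 84 days (about 9-12 weeks). The unobserved claims interval is the one from 31 May.

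**3. Each kind of change in the gap, taken through the stated rules.**
- *Stopped the study drug:* fails the self-report criterion and should be removed.
- *Switched to the other study drug:* meets the criterion. Under the synopsis the patient falls in the cohort of the drug now in use.
- *Kept the study drug and added a LAMA or ICS:* meets the criterion. The triple-therapy rule sees only baseline claims, so the patient is kept as dual therapy.
- *Reports both study drugs:* meets the criterion. The both-drug rule sees only claims up to identification. The patient is kept, and no rule says in which cohort.

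The last two routes are open.

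**4. Size, under assumption.** The documents give no rate of add-on. Let m be the share of respondents affected, with an assumed range of 2-15%.

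If they are excluded, the completes needed are 385 / (1 − m), rounded up. Starting from 385 instead, the half-width is 1.96 × √(0.25 / n), with n = 385 × (1 − m) rounded down:
- m = 2%: 393 completes, or half-width 0.0505 (n = 377)
- m = 5%: 406 completes, or 0.0513 (n = 365)
- m = 10%: 428 completes, or 0.0527 (n = 346)
- m = 15%: 453 completes, or 0.0542 (n = 327)

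If they are kept and carry no drug contrast, an assumed true difference of 10 points (45% v 55%) shrinks to 0.10 × (1 − m). With n = 385 per cohort and d the difference, power = Φ[(d − 1.96 × √(2 × 0.25 / n)) / √((p₁q₁ + p₂q₂) / n)]. At m = 0 this is (0.10 − 0.0706) / 0.0359 = 0.82, or 79%. At m = 2%, 5%, 10% and 15% it is about 78%, 75%, 71% and 66%. These figures show dilution only. If add-on differs between cohorts, the bias could go either way, and the documents do not allow it to be sized.

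**The case against.** The strongest reply is that the survey already guards the regimen. Current treatment is asked, self-reported treatment is an eligibility criterion, and the limitations sections cite it as mitigation. That stands for stopping and switching. It does not cover add-on or reporting both drugs, because the criterion asks only whether a study drug is taken.

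A reader might infer four stronger points that the documents do not support:
- *That study-drug use is checked only up to sample identification.* It is checked again by self-report at the survey.
- *That the contamination can be put at about 1-12% of a cohort.* That follows from an assumed 1-4% per month adding, switching or stopping over 25 to 99 days. It counts the two routes that self-report handles, its upper end gives every respondent the longest gap, and the monthly rate is not in the documents.
- *That add-on cannot be seen in the planned data.* The survey records current COPD treatment. The instrument is not in the documents, so nobody can say that the item would miss an added inhaler.
- *That one fill on 1 December 2017, 206 to 280 days before a survey on 25 June to 7 September, leaves use at the survey unchecked.* Reported current use is a direct check, and the protocol itself notes that a fill does not show the drug was taken. A days'-supply check is supplementary.

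Two cautions about remedies also stand. Enrollment is required only through baseline, so an absent fill in the gap means little unless the patient was still enrolled. And if add-on follows symptoms, removing these patients on later claims selects on a consequence of symptoms, possibly to a different degree in each cohort.

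**Conclusion.** The concern holds in a limited form. The both-drug and triple-therapy exclusions end with the claims window, about 3-5 weeks before Wave 1 fielding starts and 12-14 weeks before it ends. Nothing removes or classifies a respondent who still takes the study drug and has added a LAMA or ICS, or who reports both study drugs. Nor is there a rule for disagreement between claims and self-report. These respondents' current CAT and mMRC enter the primary comparison as dual therapy.

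The number affected is unknown. The loss and power figures above rest on an assumed 2-15% share and, for power, on an assumed 10-point difference. The gap rests on estimated Wave 1 dates, with final dates deferred to the SAP. The target of 385 is not in question. The change is worth making because it uses the protocol's own exclusions and a survey item already collected.

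**What to change.** **Section 3.2.1.2.** Apply the existing both-drug and triple-therapy exclusions to the survey's current-treatment item as well. State how each is read from that item, since the claims definition depends on spacing between fills. Confirm that the item lists all maintenance inhalers. State which source defines the cohort when claims and self-report disagree, and use it in 3.4.1, 4.4 and 4.5.

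**Section 3.1.6.** Extend respondents' pharmacy extraction from the end of baseline to the survey return date. As a sensitivity analysis among those still enrolled at that date, repeat the CAT and mMRC comparison (a) after excluding patients with both-drug or triple-therapy claims in the gap and, separately, (b) in those whose study-drug supply reached the survey. Report the counts by cohort. The claims-based steps belong in a sensitivity analysis because of the selection problem noted above. The survey-based exclusion may share it in part, so its counts should also be shown by cohort.

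**Cost.** No delay is expected. If Wave 2 runs one month after Wave 1, its claims window closes about 30 June 2018 and the six-month medical lag ends about the end of December. Its last surveys return in early October, and six weeks for pharmacy claims (3.3.3) ends in mid-November. Consent and data-use wording must cover the extra weeks, and enrollment must be checked through survey return. Some respondents are lost: at an assumed 5%, about 406 completes keep 385 per cohort, or the half-width widens from 0.050 to about 0.051.

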3.2 Study Population

3.2.1 Eligibility Criteria

The study will include MA health plan members with evidence of COPD in the 12 months prior to sample identification and evidence of treatment with UMEC/VI or FLUT/SAL single-inhaler dual therapy in the

six months prior to sample identification. To be included in the target study population, patients must meet the study inclusion/exclusion criteria. Potential inclusion criteria for consideration are listed below.

